6.8.1. Use of Concomitant SSRIs/SNRIs

Participants who are stable on SSRI/SNRIs as well as those not on concomitant SSRI/SNRIs at Screening may be enrolled in the study, as follows:

- Participants on an SSRI/SNRI at Screening may stay on the SSRI/SNRI as long as the following criteria are met: (1) the SSRI/SNRI is not a prohibited medication (eg,

fluvoxamine; see the prohibited medication list in the Investigator Trial Site Binder), (2) the dosing regimen remains stable with no plans to change during the course of the trial, and (3) the PTSD severity criteria outlined in the eligibility criteria ([Section 5](#)) are still met. The use of tricyclic antidepressants are prohibited.

- Participants not on an SSRI/SNRI at screening will also be enrolled as long as treatment with an SSRI/SNRI is not initiated during the course of treatment.

7. DISCONTINUATION OF STUDY INTERVENTION AND PARTICIPANT DISCONTINUATION/WITHDRAWAL

Discontinuation from study intervention does not represent discontinuation from the study ([Section 7.2](#)). Participants may discontinue from study intervention at any time for any reason, or at the discretion of the investigator. In addition, a participant may be withdrawn from study intervention by the investigator or sponsor for safety, behavioral, compliance, and/or administrative reasons.

For participants that discontinue study intervention, all effort should be made to complete the procedures listed in the Early Discontinuation Visit, Efficacy Follow-up Visit (if applicable), and Safety Follow-up Visit ([Section 1.3](#)). If the participant does not withdraw from the study, continue to follow the participant as detailed in the SoA ([Section 1.3](#)).

7.1. Discontinuation of Study Intervention

In some instances, it may be necessary for a participant to permanently discontinue study intervention. If study intervention is permanently discontinued, the participant will be requested to remain in the study and be asked to complete a 12-week efficacy follow-up. See the SoA for data to be collected at the time of discontinuation of study intervention and follow-up and for any further evaluations that need to be completed. Every effort should be made to have the participant attend an Early Discontinuation Visit and the Week 12 efficacy follow-up. For those participants who discontinue study intervention prior to Week 4, every effort should be made to have the participant complete the efficacy follow-up at Week 4 and Week 12 (see [Section 1.3](#)).

A participant must be discontinued from study intervention for any of the following reasons, or if they meet protocol stopping criteria:

- The participant requests to discontinue study intervention.
- The participant has an AE that may compromise the participant's continued participation.
- The participant has a suicide risk reported or assessed by the C-SSRS that requires intervention ([Section 8.3.6](#)).
- The participant has a positive pregnancy test ([Appendix 5](#) and [Section 8.4.5](#)).
- The participant is noncompliant with study intervention or procedures.
- The participant meets the liver chemistry stopping criteria ([Section 7.1.1](#)).
- The participant meets the QTc stopping criteria ([Section 7.1.2](#)).
- [REDACTED]
- The sponsor decides to terminate the study prior to completion.
- The investigator determines the participant should not continue on study intervention.

7.1.1. Liver Chemistry Stopping Criteria

Discontinuation of study intervention for abnormal liver tests is required by the investigator when a participant meets one of the conditions outlined in [Appendix 7](#) or in the presence of abnormal liver chemistries not meeting protocol-specified stopping rules if the investigator believes that it is in best interest of the participant.

7.1.2. QTc Stopping Criteria

If a clinically significant finding is identified in a particular study participant (including, but not limited to a measured QT interval corrected using QTcF of > 500 msec) after enrollment and confirmed with a repeat (second) ECG, the investigator or qualified designee will discontinue the participant from the study and arrange for appropriate follow-up, including repeat ECGs as indicated. This review of the ECG printed at the time of collection must be documented. Any new clinically relevant finding should be reported as an AE.

7.1.3. [REDACTED]

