7.2. Participant Discontinuation/Withdrawal from the Study

A participant may withdraw from the study at any time at his/her own request or may be withdrawn at any time at the discretion of the investigator for safety, behavioral, or compliance reasons. This is expected to be uncommon.

If the participant is discontinued from study intervention, they will be asked to continue with follow-up efficacy visits. In this case, the participant will undergo the efficacy follow-up, as shown in the SoA ([Section 1.3](#)) and described in [Section 7.1](#).

If the participant is discontinued both from the study intervention, which will be returned to the clinical site, and from the study, an early discontinuation visit should be conducted (if possible) at the time of discontinuation, as shown in the SoA ([Section 1.3](#)). Refer to the SoA ([Section 1.3](#)) for data to be collected at the time of study discontinuation and follow-up and for any further evaluations that need to be completed.

If the participant withdraws consent for disclosure of future information, the sponsor may retain and continue to use any data collected before such a withdrawal of consent.

If a participant withdraws from the study, he/she may request destruction of any samples taken and not tested, and the investigator must document this in the site study records.

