8.3.3. Electrocardiograms

Triplicate 12-lead ECGs will be obtained as outlined in the SoA (see [Section 1.3](#)) using an ECG machine that automatically calculates the heart rate and measures PR, QRS, QT, and corrected QT (QTc) intervals. Refer to [Section 7.1.2](#) for QTc withdrawal criteria and any additional QTc readings that may be necessary.

Electrocardiograms will be reviewed, initially interpreted, signed, and dated by the investigator or a designated physician after each ECG collection. All ECGs (with the exception of ECGs for participants who are screen failures) will be transmitted to a designated central ECG laboratory. A cardiologist at the central ECG laboratory will conduct a full over-read. A report based on data from this over-read will be issued to the site.

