8.3.5. Pregnancy Testing

Refer to [Section 5.1](#) for pregnancy testing entry criteria.

Pregnancy testing (urine or serum as required by local regulations) should be conducted as specified in the SoA ([Section 1.3](#)). Urine pregnancy testing will be done by dipstick at the site. At Screening, clinical sites will also do a serum pregnancy that will be sent to the central lab. At all other visits, a serum pregnancy can be conducted as needed (ie, if the site obtains a positive urine pregnancy test).

Pregnancy testing (urine or serum as required by local regulations) should be conducted at the end of relevant systemic exposure.

Additional serum or urine pregnancy tests may be performed, as determined necessary by the investigator or required by local regulation, to establish the absence of pregnancy at any time during participation in the study.

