8.4.5. Pregnancy

Details of all pregnancies in female participants and, if indicated, female partners of male participants will be collected after the start of study intervention and until 30 days after the last dose of study intervention.

If a pregnancy is reported, the investigator will record pregnancy information on the appropriate form and submit it to the sponsor within 24 hours of learning of the female participant or female partner of male participant (after obtaining the necessary signed informed consent from the female partner) pregnancy.

While pregnancy itself is not considered to be an AE or SAE, any pregnancy complication or elective termination of a pregnancy for medical reasons will be reported as an AE or SAE.

Abnormal pregnancy outcomes (eg, spontaneous abortion, fetal death, stillbirth, congenital anomalies, ectopic pregnancy) are considered SAEs and will be reported as such.

The participant/pregnant female partner will be followed to determine the outcome of the pregnancy. The investigator will collect follow-up information on the participant /pregnant female partner and the neonate, and the information will be forwarded to the sponsor. The pregnancy of a participant or a female partner of a male participant will be followed until the

outcome of the pregnancy is known and, in the case of a live birth, for 6 months following the birth of the child. The Infant Follow-up Form should be used to report information regarding the status of the infant.

Any post-study pregnancy-related SAE considered reasonably related to the study intervention by the investigator will be reported to the sponsor as described in [Section 8.4.4](#). While the investigator is not obligated to actively seek this information in former study participants/pregnant female partner, he or she may learn of an SAE through spontaneous reporting.

Any female participant who becomes pregnant while participating in the study will be withdrawn from the study.

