
A specialist or hepatology consultation is recommended.
 
If $ALT \geq 3 \times ULN$ AND total bilirubin $< 2 \times ULN$ and INR ≤ 1.5:
 
Repeat liver chemistry tests (include ALT, AST, alkaline phosphatase, total bilirubin and INR) and perform liver chemistry follow-up assessments within 24 to 72 hours.
 
Monitor participants weekly until liver chemistry abnormalities resolve, stabilize, or return to baseline.
 
Permanently discontinue study intervention and continue participant in the study for any protocol-specified follow-up assessments.
	
Serum acetaminophen adduct assay, when available, to assess potential acetaminophen contribution to liver injury in participants with definite or likely acetaminophen use in the preceding week.
 
Liver imaging (ultrasound, magnetic resonance, or computerized tomography) and/or liver biopsy to evaluate liver disease. Provide liver imagine results via email to [contact].
 
Liver biopsy may be considered and discussed with local specialist if available:
 
In participants when serology raises the possibility of autoimmune hepatitis.
 
In participants when suspected drug-induced liver injury progresses or fails to resolve on withdrawal of study intervention.
 
In participants with acute or chronic atypical presentation
 
If liver biopsy conducted, provide liver imaging results via email to [contact].

^a Serum bilirubin fractionation should be performed if testing is available. If serum bilirubin fractionation is not immediately available, discontinue study intervention if $ALT \geq 3 \times ULN$ and total bilirubin $\geq 2 \times ULN$.

Additionally, if serum bilirubin fractionation testing is unavailable, **record the absence/presence of detectable urinary bilirubin on dipstick which** is indicative of direct bilirubin elevations suggesting liver injury.

^b All events of $ALT \geq 3 \times ULN$ and total bilirubin $\geq 2 \times ULN$ ($> 35\%$ direct bilirubin) or $ALT \geq 3 \times ULN$ and INR > 1.5 may indicate severe liver injury (**possible “Hy’s Law”**) and **must be reported to sponsor in an expedited manner and as an SAE if SAE criteria met**. The INR stated threshold value will not apply to participants receiving anticoagulants.

^c New or worsening symptoms believed to be related to liver injury (such as fatigue, nausea, vomiting, right upper quadrant pain or tenderness, or jaundice) or hypersensitivity (such as fever, rash or eosinophilia).

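### Protocol 7.1 asks participants stopped for QTc or pregnancy to stay for the Week 12 efficacy follow-up, but 7.1.2 and 8.4.5 remove them from the study

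*Protocol*

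**What the plan says.** Protocol section 7 treats stopping study intervention and leaving the study as different events. Section 7.1 then says that after permanent discontinuation of study intervention "the participant will be requested to remain in the study and be asked to complete a 12-week efficacy follow-up". Those who stop before Week 4 are also to be seen at Week 4. The list of mandatory reasons for stopping study intervention in 7.1 includes the QTc criteria, citing 7.1.2, and a positive pregnancy test, citing Appendix 5 and 8.4.5. No exception to the request to remain is attached to either.

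The cited sections go further. For a confirmed clinically significant finding, including but not limited to QTcF above 500 msec, the investigator under 7.1.2 "will discontinue the participant from the study and arrange for appropriate follow-up". Section 8.4.5 says: "Any female participant who becomes pregnant while participating in the study will be withdrawn from the study".

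For liver events, Appendix 7 (Table 7) follows the pattern of 7.1: "Permanently discontinue study intervention and continue participant in the study for any protocol-specified follow-up assessments".

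On the analysis side, the primary estimand (Protocol section 3) applies treatment policy to all intercurrent events. SAP 5.1 says the protocol intends efficacy data to be collected whatever intercurrent event occurs. SAP 7.6 and 9.1.2 include data obtained after treatment discontinuation in the main analysis.

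**The concern.** A site with a confirmed QTc finding or a pregnancy has two instructions that cannot both be followed: keep the participant for Week 12 efficacy follow-up, or take the participant out of the study. The drug stops either way, and the early discontinuation and safety follow-up visits apply either way. What depends on the reading is the efficacy follow-up visit, because footnote b of the Schedule of Activities restricts it to participants who stop study intervention but stay in the study.

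A treatment-policy estimand needs the Week 12 outcome of people who stopped treatment. A rule that withdraws them for a safety reason leaves that outcome missing by design, where 7.1 would have tried to collect it.

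**Working it through.** No figure in the plan bears directly on this point, so the check is mainly a comparison of text, followed by the consequence for the data and an illustration of size.

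**1. Which instruction applies**

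- 7.1: stop study intervention and ask the participant to remain. It names QTc and pregnancy and states no exception.
- 7.1.2: stop participation in the study. The only stated content of its follow-up is repeat ECGs.
- 8.4.5: withdraw from the study. Follow-up concerns the pregnancy outcome and the infant.
- Section 7: "If the participant does not withdraw from the study, continue to follow the participant as detailed in the SoA". This covers people who stay, but does not say whether QTc or pregnancy cases are among them.
- Appendix 7: stop study intervention and keep the participant in the study.

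**2. What is lost under 7.1.2 or 8.4.5**

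- SAP 7.2.3: CAPS-5 is not collected at the safety follow-up visit. For a removed participant, the last scheduled CAPS-5 is the early discontinuation visit.
- SAP Table 3: the CAPS-5 windows are Days 1 to 56 for Week 4 and Days 57 to 112 for Week 12.
- SAP Table 5 maps the early discontinuation CAPS-5 by those windows, and SAP 7.2.3 leaves an empty window missing.
- An early discontinuation CAPS-5 on or before Day 56 therefore counts as Week 4, and Week 12 is missing. From Day 57 it counts as Week 12 and nothing is lost.
- Removal at Week 1 (Day 7 ± 2, so Days 5 to 9) or Week 4 (Day 28 ± 2, so Days 26 to 30) falls before the boundary. Week 8 (Day 56 ± 2) straddles it. A finding at the Week 12 visit costs nothing, since CAPS-5 is due there.
- CGI-S and PGI-S are collected at safety follow-up, but that visit comes too early. If drug stops by Day 30, it falls by Day 30 + 14 + 5 = Day 49, before the Week 12 window for these scales opens on Day 71. Early removals lose those Week 12 values too.

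I do not count the scheduled ECG or pregnancy tests that could trigger removal. The layout of SAP Table 3 and of the ECG row in the Schedule of Activities is not reliable in the text I worked from. Protocol 8.3.5 also allows unscheduled detection: "Additional serum or urine pregnancy tests may be performed, as determined necessary by the investigator".

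**3. Size per case (illustration)**

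Inputs: planned Week 12 completers of 75 (placebo and 4 mg) and 38 (0.3 mg), and a planned difference of 6 points, from Protocol 9.2. Assumption: the lost value would have been 6 points away from its prediction under missing at random.

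Adding one observation to *n* observed values moves the arm mean by about *r*/(*n* + 1), because the added value also feeds the implicit prediction for others who are missing:

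- 75 observed: 6/76 = 0.08 points.
- 38 observed: 6/39 = 0.15 points.

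The shift scales with the assumed 6 points. It also depends on the number observed, and Full Analysis Set 1 excludes Site 1865 and undosed participants. It is not a bound.

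**4. Power**

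The plan already allows for 270 − 188 = 82 participants without 12 weeks of data. A participant stopped early for QTc or pregnancy is one of these under either reading, so no further loss of power follows.

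**The case against.** The strongest reply is that the texts can be read together. The list in 7.1 says when study intervention must stop, and leaving the study also stops it. Sections 7.1.2 and 8.4.5 are specific and mandatory, while the text in 7.1 is a general request. Section 7.2 provides for study withdrawal: a participant "may be withdrawn at any time at the discretion of the investigator for safety, behavioral, or compliance reasons". Section 8.3.3 refers the reader to 7.1.2 "for QTc withdrawal criteria and any additional QTc readings that may be necessary", which suggests that withdrawal was meant. A sponsor may choose to withdraw such participants, and the liver rule does not oblige it to treat other events alike.

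Part of this stands. The documents do not prove which side is the slip, and writing the exception into 7.1 would also resolve the conflict. But 7.2 is discretionary where 7.1.2 and 8.4.5 are not, and no text states an override. Even on that reading, SAP 5.1 and the estimand still say that data are collected whatever the intercurrent event, so a correction is needed somewhere.

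It also stands that the effect is already handled. Early discontinuation CAPS-5 values enter the main analysis, the mixed model treats the remaining gap as missing at random, and the tipping-point and control-based analyses (SAP 9.1.3) test that assumption.

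Two stronger readings are tempting. A reader might infer that this conflict biases the primary result or costs power. With no QTc or pregnancy rate in the documents, and with the 30% dropout already planned, that is not supported. A reader might also link it to SAP 7.7, which drops the time-dependent multiple imputation because little efficacy follow-up was collected after intercurrent events. SAP 7.7 does not say why collection was limited, and nothing ties it to these two rules.

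**Conclusion.** The inconsistency is real and is in the current protocol text. For QTc and pregnancy cases, 7.1 asks for retention and the sections it cites require removal. Where removal is followed and the last CAPS-5 falls by Day 56, there is no Week 12 value for the treatment-policy analysis.

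Severity is minor. Few cases are expected, since entry excludes QTcF above 450 msec (men) or 470 msec (women) and contraception is required. Retention would not recover every value, because not everyone asked to stay will return. The illustrative shifts rest on the assumed 6-point departure and the planned completer numbers, and they are small beside the planned difference. I am confident about the conflict itself. The number of affected participants cannot be stated from the documents.

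**What to change.** In 7.1.2 and 8.4.5, replace removal from the study with permanent discontinuation of study intervention. Add that the participant is asked to stay for the efficacy and safety follow-up visits under 7.1 and footnote b of the Schedule of Activities, in line with Appendix 7. Keep the repeat-ECG follow-up, the pregnancy-outcome follow-up and the withdrawal options in 7.2 as they are.

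If the sponsor does intend study withdrawal for these cases, leave 7.1.2 and 8.4.5 alone and state the exception in 7.1 and in SAP 5.1.

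The cost is two sentences, in a clarification letter or the next amendment, and one or two extra visits (Week 4, Week 12 or both) for each affected participant who agrees to stay. The documents do not say whether follow-up was still open when the SAP was dated (12 December 2023). If it had closed, the clinical study report should record how such cases were handled, and the wording should be corrected before it is reused in a later protocol.

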7.1.4. Temporary Discontinuation/Study Intervention Interruption

If a participant must temporarily interrupt study intervention for any reason, the Medical Monitor should be consulted to determine whether the participant will continue in the study.

7.2. Participant Discontinuation/Withdrawal from the Study

A participant may withdraw from the study at any time at his/her own request or may be withdrawn at any time at the discretion of the investigator for safety, behavioral, or compliance reasons. This is expected to be uncommon.

If the participant is discontinued from study intervention, they will be asked to continue with follow-up efficacy visits. In this case, the participant will undergo the efficacy follow-up, as shown in the SoA ([Section 1.3](#)) and described in [Section 7.1](#).

If the participant is discontinued both from the study intervention, which will be returned to the clinical site, and from the study, an early discontinuation visit should be conducted (if possible) at the time of discontinuation, as shown in the SoA ([Section 1.3](#)). Refer to the SoA ([Section 1.3](#)) for data to be collected at the time of study discontinuation and follow-up and for any further evaluations that need to be completed.

If the participant withdraws consent for disclosure of future information, the sponsor may retain and continue to use any data collected before such a withdrawal of consent.

If a participant withdraws from the study, he/she may request destruction of any samples taken and not tested, and the investigator must document this in the site study records.

7.3. Lost to Follow-up

A participant will be considered lost to follow-up if he or she repeatedly fails to return for scheduled visits and is unable to be contacted by the study site.

The following actions must be taken if a participant fails to return to the clinic for a required study visit:

- The site must attempt to contact the participant and reschedule the missed visit as soon as possible.
- The site must counsel the participant on the importance of maintaining the assigned visit schedule and ascertain whether or not the participant wishes to and/or should continue in the study.
- Before a participant is deemed lost to follow-up, the investigator or designee must make every effort to regain contact with the participant (where possible, 3 telephone calls and, if necessary, a certified letter to the participant's last known mailing address or local equivalent methods). After trying to contact the participant, the investigator should reach out to the contact provided by the participant. These contact attempts should be documented in the participant's medical record.
- Should the participant continue to be unreachable, he/she will be considered to have withdrawn from the study and lost to follow-up.
 - The participant is not considered lost to follow-up until the last scheduled visit for that individual participant.
 - The amount of missing data for an individual participant will be managed via the data handling guidelines for the study.

Discontinuation of specific sites or of the study as a whole are handled as part of [Study and Site Start and Closure Section 10.1.9](#).

